## Appendix 2. Clinical Laboratory Tests

---

### Safety Laboratory Tests

Hematology a	Clinical Chemistry a
Hematocrit	Sodium
Hemoglobin	Potassium
Erythrocyte count (RBC)	Bicarbonate
Mean cell volume	Chloride
Mean cell hemoglobin	Calcium (total)
Mean cell hemoglobin concentration	Calcium (ionized)
Leukocytes (WBC)	Magnesium
Absolute counts of	Phosphate
Neutrophils	Glucose
Lymphocytes	Blood urea
Monocytes	Total protein
Eosinophils	Albumin
Basophils	Total bilirubin
Platelets	Alkaline phosphatase (ALP)
	Aspartate aminotransferase (AST)
Urinalysis a	Alanine aminotransferase (ALT)
Specific gravity	Creatinine
Ph	Serology b
Protein	Hepatitis B surface antigen
Glucose	Hepatitis C antibody
Ketones	HIV
Bilirubin	Pregnancy Tests
Urobilinogen	Pregnancy test c
Blood	FSH d
Nitrite	
Leukocytes	
Microscopy e	

Abbreviations: FSH = follicle-stimulating hormone; HIV = human immunodeficiency virus; RBC = red blood cell; WBC = white blood cell.

- a Performed at screening, Predose Day 1 Period 1, 1 hour postdose (IV period) and follow-up. Fasting clinical laboratory tests at screening and Predose Day 1 Period 1.
- b Only at screening. This test will not be performed if results of the same test have been obtained from the subject within the past 6 months.
- c A blood test for pregnancy will be done at screening, and a urine pregnancy test will be done at times indicated in the Schedule of Activities (Section 2).
- d Only at screening in women for assessment of menopause status if necessary.
- e If clinically indicated, per investigator's discretion.

Note: Results of these assays will be validated by the local laboratory at the time of testing. Additional tests may be performed or auto-calculated by the laboratory as part of its standard panel that cannot be removed. Some of the above parameters are calculated from measured values. Omission of calculated values will not be considered as a protocol violation.

---

## Appendix 3. Study Governance, Regulatory, and Ethical Considerations

---

### ***Informed Consent***

The investigator is responsible for

- ensuring that the subject understands the nature of the study, the potential risks and benefits of participating in the study, and that their participation is voluntary.
- ensuring that informed consent is given by each subject or legal representative. This includes obtaining the appropriate signatures and dates on the ICF prior to the performance of any protocol procedures and prior to the administration of IP.
- answering any questions the subject may have throughout the study and sharing in a timely manner any new information that may be relevant to the subject's willingness to continue his or her participation in the study.
- providing a copy of the ICF to the participant or the participant's legal representative and retaining a copy on file.

### ***Recruitment***

Study-specific recruitment material should be approved by Lilly.

### ***Ethical Review***

The investigator or appropriate local representative must give assurance that the ERB was properly constituted and convened as required by International Council for Harmonisation (ICH) guidelines and other applicable laws and regulations.

Documentation of ERB approval of the protocol and the ICF must be provided to Lilly before the study may begin at the CRU. Lilly or its representatives must approve the ICF before it is used at the CRU. All ICFs must be compliant with the ICH guidelines on GCP.

The CRU's ERB(s) should be provided with the following:

- the current IB and updates during the course of the study
- ICF
- relevant curricula vitae

### ***Regulatory Considerations***

This study will be conducted in accordance with the protocol and with

- 1) consensus ethics principles derived from international ethics guidelines, including the Declaration of Helsinki and Council for International Organizations of Medical Sciences International Ethical Guidelines
- 2) applicable ICH GCP guidelines

- 3) applicable laws and regulations

Some of the obligations of the sponsor will be assigned to a third-party organization.

### ***Protocol Signatures***

The sponsor's responsible medical officer will approve the protocol, confirming that, to the best of his or her knowledge, the protocol accurately describes the planned design and conduct of the study.

After reading the protocol, the principal investigator will sign the protocol signature page and send a copy of the signed page to a Lilly representative.

### ***Final Report Signature***

The investigator or designee will sign the clinical study report for this study, indicating agreement with the analyses, results, and conclusions of the report.

The sponsor's responsible medical officer and statistician will sign/approve the final clinical study report for this study, confirming that, to the best of his or her knowledge, the report accurately describes the conduct and results of the study.

### ***Data Quality Assurance***

To ensure accurate, complete, and reliable data, Lilly or its representatives will do the following:

- provide instructional material to the study sites, as appropriate.
- provide training to instruct the investigators and study coordinators. This training will give instruction on the protocol, the completion of the CRFs, and study procedures.
- make periodic visits to the study site.
- be available for consultation and stay in contact with the study site personnel by mail, telephone, and/or fax.
- review and evaluate CRF data and/or use standard computer edits to detect errors in data collection.
- conduct a quality review of the database.

In addition, Lilly or its representatives will periodically check a sample of the subject data recorded against source documents at the CRU. The study may be audited by Lilly and/or regulatory agencies at any time. Investigators will be given notice before an audit occurs.

The investigator will keep records of all original source data. This might include laboratory tests, medical records, and clinical notes. If requested, the investigator will provide the sponsor, applicable regulatory agencies, and applicable ERBs with direct access to the original source documents.

***Data Collection Tools/Source Data***

An electronic data capture system will be used in this study. The CRU must define and retain all source records and must maintain a record of any data where source data are directly entered into the data capture system.

***Data Protection***

Data systems used for the study will have controls and requirements in accordance with local data protection law.

The purpose and use of subject personal information collected will be provided in a written document to the subject by the sponsor.

***Study and Site Closure******Discontinuation of Study Sites***

Clinical research unit participation may be discontinued if Lilly, the investigator, or the ERB of the CRU judges it necessary for medical, safety, regulatory, or other reasons consistent with applicable laws, regulations, and GCP.

***Discontinuation of the Study***

The study will be discontinued if Lilly judges it necessary for medical, safety, regulatory, or other reasons consistent with applicable laws, regulations, and GCP.

---

## Appendix 4. Blood Sampling Summary

---

This table summarizes the approximate number of venipunctures and blood volumes for all blood sampling (screening, safety laboratories, and bioanalytical assays) during the study.

### Protocol I8B-MC-ITRT Sampling Summary

Purpose	Blood Volume per Sample (mL)	Number of Blood Samples	Total Volume (mL)
Screening tests a,b	17	1	17
Clinical laboratory tests a,b	1×11 (fasting)	1	29
	1×9 (nonfasting)	2	
Pharmacokinetic samples serum insulin lispro	1	22 samples × 4 periods = 88	88
Pharmacokinetic samples plasma treprostинil	2	4 samples × 1 period = 4	8
C-peptide samples	2	12 samples × 4 periods = 48	96
Blood for glucose	0.2	76 samples × 4 periods = 304	60.8
Blood discard for cannula patency	0.25	76 samples × 4 periods = 304	76
Immunogenicity	5	3	15
Pharmacogenetics	10	1	10
Total for clinical purposes			399.8
Total for clinical purposes rounded up to the nearest 10 mL			400

a Additional samples may be drawn if needed for safety purposes.

b Fasting clinical laboratory tests at screening, and Predose Day 1 Period 1.

---

**Appendix 5. Protocol Amendment I8B-MC-ITRT(a)  
Summary****Effect of Injection Site on the Relative and Absolute  
Bioavailability of Single Dose of LY900014 in Healthy  
Subjects**

---

## Overview

Protocol I8B-MC-ITRT [Effect of Injection Site on the Relative and Absolute Bioavailability of Single Dose of LY900014 in Healthy Subjects] has been amended. The new protocol is indicated by Amendment (a) and will be used to conduct the study in place of any preceding version of the protocol.

The overall changes and rationale for the changes made to this protocol are as follows:

- The sample size was adjusted to ensure adequate precision to estimate the 90% CI for the ratio for SC injection into the thigh and deltoid, compared to the abdomen.
- The arm injection site was changed to deltoid to ensure consistency in protocol language.
- PK and GD parameters (time to early half-maximal plasma concentration [early 50%  $t_{max}$ ], time to late half-maximal drug concentration [late 50%  $t_{max}$ ], time to half-maximal GIR before  $t_{R_{max}}$  [early 50%  $t_{R_{max}}$ ], time to half-maximal GIR after  $t_{R_{max}}$  [late 50%  $t_{R_{max}}$ ], time to onset of insulin action [ $T_{onset}$ ], and  $G_{tot}$  over 10 hours [ $G_{tot[0-10h]}$ ], partial glucose AUCs, such as total amount of glucose infused over 30 minutes, 1 or 2 hours) were removed as they were not required for the statistical analysis to support the objectives of the study. There is no change to primary and secondary endpoints.
- The criterion to include subjects with body weight  $\geq 45$  kg and hemoglobin level of  $\geq 12.5$  g/dL at screening was included based on recommendation of Domain Specific Review Board (DSRB), Singapore. The rationale given was that a blood volume of approximately 400 mL or more would be withdrawn per subject throughout the study.

## Revised Protocol Sections

Note:	All deletions have been identified by <del>strike-throughs</del> .
	All additions have been identified by the use of underscore .

The numbering system used for inclusion and exclusion criteria provides a unique number for each criterion and allows for efficiency in data collection.

In case an amendment to the protocol adds a criterion, that criterion will receive the next available number, regardless of whether it is an inclusion or exclusion criterion.

### 1 Protocol Synopsis

#### Rationale:

The primary objective of this study is therefore to compare the bioavailability of insulin lispro following administration of the commercial formulation of LY900014 at 3 different injection sites SC in the abdominal wall, thigh, and ~~arm~~ deltoid. In addition, the intravenous (IV) administration will serve as the reference to determine the absolute bioavailability of SC injections into the ~~arm~~deltoid, thigh or abdomen and GD activity.

#### Number of Subjects:

Up to ~~24~~ 28 healthy men and women may be enrolled to target at least ~~16~~ 22 subjects complete the study.

#### 3.1 Study Rationale

The primary objective of this study is therefore to compare the bioavailability of insulin lispro following administration of the commercial formulation of LY900014 at 3 different injection sites SC in the abdominal wall, thigh, and ~~arm~~ deltoid. In addition, the intravenous (IV) administration will serve as the reference to determine the absolute bioavailability of SC injections into the ~~arm~~deltoid, thigh, or abdomen and GD activity.

#### 5.1 Overall Design

This is a Phase 1, single-center, open-label, 4-period, randomized, crossover, up to 10-hour euglycemic clamp study in approximately ~~24~~28 healthy subjects to compare the insulin lispro PK and GD of LY900014 after SC administration of a 15-U dose at 3 different injection sites and a single IV bolus injection of 15 U.

#### 5.2 Number of Participants

A total of ~~24~~28 subjects may be enrolled so that at least ~~16~~22 subjects complete the study.

If subjects discontinue from the study before completion of all 4 study periods, replacement subjects may be enrolled up to ~~24~~28 subjects following agreement between the investigator and the sponsor.

**6.1 Inclusion Criteria**

[3] have a body weight of  $\geq 45$  kg, and body mass index (BMI) of 18.0 to 30.0 kg/m^2, inclusive

**6.2 Exclusion Criteria**

Additional inclusion criterion:

[27] have a hemoglobin level of  $\geq 12.5$  g/dL at screening

**10.1. Sample Size Determination**

Up to 24-28 subjects may be enrolled to ensure that at least 16-22 subjects complete the study. Sixteen Twenty-two completing subjects will provide at least 90% power to show the estimated 2-sided 90% confidence intervals (CIs) of the ratios of geometric means for area under the concentration versus time curve (AUC) from time zero to infinity (AUC[0- $\infty$ ]) after SC injection into the thigh and deltoid, compared to the abdomen, to be within approximately 20% of the geometric mean ratio estimate 0.8 to 1.25 when the observed ratio is 1. This calculation is based on the assumption of a log-normal distribution and an estimate of intrasubject log-scale standard deviation of 0.2. There is also approximately 86% power for the comparisons between injection sites for maximum observed serum concentration (Cmax), assuming an intrasubject log-scale standard deviation of 0.35.

**10.3.2.1 Pharmacokinetic Parameter Estimation**

Free serum insulin lispro concentrations will be used to calculate several PK parameters, including maximum observed drug concentration (Cmax), time of maximum observed drug concentration (tmax), t1/2, time to early half maximal plasma concentration (early 50% tmax), time to late half maximal drug concentration (late 50% tmax), and area under the concentration versus time curve from time zero to time t, where t is the last time point with a measurable concentration (AUC[0-tlast]), AUC from time zero to 10 hours (AUC[0-10h]), area under the concentration versus time curve from time zero to infinity (AUC[0- $\infty$ ]), apparent total body clearance of drug calculated after extra-vascular administration (CL/F), and apparent volume of distribution during the terminal phase after extra-vascular administration (Vz/F) will be determined.

**10.3.3.1 Glucodynamic Parameter Estimation**

A locally weighted scatterplot smoothing (LOESS) function will be applied to all individual GIR versus time profiles in each treatment group and age group using S-PLUS software (version 8.2). The fitted data for each subject will be used to calculate the following GD parameters: maximum GIR (Rmax), time to Rmax (tRmax), time to half maximal GIR before tRmax (early 50% tRmax), time to half maximal GIR after tRmax (late 50% tRmax), time to onset of insulin action (Tonset), and total amount of glucose infused (Gtot), and Gtot over 10 hours (Gtot[0-10h]). Additional GD parameters partial glucose AUCs, such as total amount of glucose infused over 30 minutes, 1 or 2 hours may be computed as necessary. The values of these GD parameters will

be summarized by treatment group through descriptive statistics. Mean LOESS fits of GIR versus time profiles will be generated.

Leo Document ID = 3d691570-b5ac-4e8d-ac55-5ebcfe66512e

Approver: PPD

Approval Date & Time: 14-Jul-2017 12:38:59 GMT

Signature meaning: Approved

Approver: PPD

Approval Date & Time: 14-Jul-2017 13:11:04 GMT

Signature meaning: Approved

2. ABBREVIATIONS

Abbreviations pertain to the Statistical Analysis Plan (SAP) only (not the tables, figures and listings [TFLs]).

AE	Adverse event
AUC	Area under the concentration versus time curve
AUC(0-10h)	Area under the concentration versus time curve from time zero to 10 hours
AUC(0-t _{last})	Area under the concentration versus time curve from time zero to time t, where t is the last time point with a measurable concentration
AUC(0-∞)	Area under the concentration versus time curve from time zero to infinity
C _{max}	Maximum observed drug concentration
CI	Confidence interval
CL	Total body clearance of drug calculated after intravenous administration
CRF	Case Report Form
CSR	Clinical Study Report
CRU	Clinical Research Unit
CV	Coefficient of variation
EC	Early Clinical
ECG	Electrocardiogram
e.g.	For example (Latin: exempli gratia)
G _{tot}	Total amount of glucose infused
GD	Glucodynamic
GIR	Glucose infusion rate
ICH	International Council on Harmonisation
IV	Intravenous
LOESS	Locally weighted scatterplot smoothing
LS	Least square
MedDRA	Medical Dictionary for Regulatory Activities
PK	Pharmacokinetic
R _{max}	Maximum glucose infusion rate

SAP	Statistical Analysis Plan
SC	Subcutaneous
SD	Standard deviation
TFLs	Tables, Figures, and Listings
$t_{1/2}$	Half-life associated with the terminal rate constant (λ_z) in non-compartmental analysis
t_{\max}	Time of maximum observed drug concentration
tR_{\max}	Time to R_{\max}
V	Volume of distribution
V_z/F	Apparent volume of distribution during the terminal phase after extra-vascular administration
WHO	World Health Organization

3. INTRODUCTION

This SAP has been developed after review of the Clinical Study Protocol (final version dated 24 May 2017 and amendment (a) dated 14 July 2017).

This SAP describes the planned analysis of the safety, tolerability, pharmacokinetic (PK) and glucodynamic (GD) data from this study. A detailed description of the planned TFLs to be presented in the clinical study report (CSR) is provided in the accompanying TFL shell document.

The intent of this document is to provide guidance for the statistical and PK analyses of data. In general, the analyses are based on information from the protocol, unless they have been modified by agreement between Eli Lilly and Company and CCI. A limited amount of information concerning this study (e.g., objectives, study design) is given to help the reader's interpretation. This SAP must be signed off prior to first subject administration for this study. When the SAP and TFL shells are agreed upon and finalized, they will serve as the template for this study's CSR.

This SAP supersedes the statistical considerations identified in the protocol; where considerations are substantially different, they will be so identified. If additional analyses are required to supplement the planned analyses described in this SAP, they may be performed and will be identified in the CSR. Any substantial deviations from this SAP will be agreed upon between Eli Lilly and Company and CCI and identified in the CSR. Any minor deviations from the TFLs may not be documented in the CSR.

This SAP is written with consideration of the recommendations outlined in the International Council on Harmonisation (ICH) E9 Guideline entitled Guidance for Industry: Statistical Principles for Clinical Trials¹ and the ICH E3 Guideline entitled Guidance for Industry: Structure and Content of Clinical Study Reports².

4. STUDY OBJECTIVES

4.1 Primary Objectives

- To determine the relative bioavailability of insulin lispro from LY900014 after SC injection into the thigh and deltoid compared to the abdomen in healthy subjects.
- To determine absolute bioavailability of insulin lispro following SC administrations of LY900014 into the thigh, deltoid, and abdomen compared to IV administration of LY900014 in healthy subjects.

4.2 Secondary Objectives

- To evaluate the tolerability of LY900014 in healthy subjects.
- To evaluate the GD during euglycemic clamp procedure of LY900014 after SC injection into the abdomen, thigh, and deltoid and IV in healthy subjects.

4.3 Exploratory Objectives

- To evaluate C-peptide levels after administration of LY900014.
- To determine plasma concentrations of the excipient, treprostinil, following administration of a single, IV 15-U dose of LY900014 in healthy subjects.

5. STUDY DESIGN

This is a Phase 1, single-center, open-label, 4-period, randomized, crossover, up to 10-hour euglycemic clamp study in approximately 28 healthy subjects to compare the insulin lispro PK and GD of LY900014 after SC administration of a 15-U dose at 3 different injection sites and a single IV bolus injection of 15 U. The SC injection sites are the abdomen, thigh, and deltoid.

Subjects will be required to attend the clinical research unit (CRU) on at least 6 occasions:

- screening visit (may occur up to 28 days before randomization)
- four treatment visits for the clamp procedure (study Periods 1 to 4) with a wash-out period of ≥ 3 days between discharge and the next admission to the CRU
- follow-up visit (at least 14 days after last dose), or early discontinuation.

Each subject will be randomly assigned to a treatment sequence and will be administered single doses of 15 U of LY900014 (on 4 occasions).

Subjects will be admitted to the CRU on the evening before each dosing day and will remain in the CRU for the duration of the clamp period and until discharge by the investigator. Subjects are expected to fast for at least 8 hours before each dose. Following dose administration, each subject will undergo a euglycemic clamp procedure of up to 10 hours. Upon completion of the clamp procedures, the subjects will be provided a meal and observed overnight. Subjects will be discharged from the CRU the next day after medical assessments.

Study governance considerations are described in detail in Appendix 3 of the protocol.

[figure not shown]

Figure ITRT.1 illustrates the study design.

Treatment Sequence	Period 1	Period 2	Period 3	Period 4
1	LY900014 Abdomen	LY900014 Thigh	LY900014 Deltoid	LY900014 IV
2	LY900014 Deltoid	LY900014 Abdomen	LY900014 IV	LY900014 Thigh
3	LY900014 IV	LY900014 Deltoid	LY900014 Thigh	LY900014 Abdomen
4	LY900014 Thigh	LY900014 IV	LY900014 Abdomen	LY900014 Deltoid

Abbreviation: IV = intravenous.

Note: Subcutaneous injection sites are the abdomen, deltoid and thigh.

Figure ITRT.2 illustrates the treatment sequences.

6. TREATMENTS

The following is a list of the study treatment names that will be used in the TFLs.

Study Treatment Name	Treatment order in TFL
15 U LY900014 Abdomen	1
15 U LY900014 Thigh	2
15 U LY900014 Deltoid	3
15 U LY900014 IV	4

7. SAMPLE SIZE JUSTIFICATION

Up to 28 subjects may be enrolled to ensure that at least 22 subjects complete the study. Twenty-two completing subjects will provide estimated 2-sided 90% confidence intervals (CIs) of the ratios of geometric means for AUC[0-∞] after SC injection into the thigh and deltoid, compared to the abdomen, to be within approximately 0.8 to 1.25 when the observed ratio is 1. This calculation is based on the assumption of a log-normal distribution and an estimate of intrasubject log-scale standard deviation of 0.2.

If subjects discontinue from the study before completion of all 4 study periods, replacement subjects may be enrolled up to 24 subjects following agreement between the investigator and the sponsor.

A replacement subject will be assigned the treatment sequence of the discontinued subject and complete that treatment sequence in its entirety.

8. DEFINITION OF ANALYSIS POPULATIONS

The "Safety" population will consist of all subjects who received at least one dose of study drug.

The "Pharmacokinetic" population will consist of those subjects who receive at least 1 dose of study drug and have measurable insulin lispro concentrations and had evaluable PK data.

The “Glucodynamic” population will consist of those subjects who complete at least 1 clamp procedure.

All protocol deviations that occur during the study will be considered for their severity/impact and will be taken into consideration when subjects are assigned to analysis populations.

9. STATISTICAL METHODOLOGY

9.1 General

Data listings will be provided for all data that is databased. Summary statistics and statistical analysis will only be presented for data where detailed in this SAP. For continuous data, summary statistics will include the arithmetic mean, arithmetic standard deviation (SD), median, min, max and N; for log-normal data (e.g. the PK parameters: AUCs and C_{max}) the geometric mean and geometric coefficient of variation (CV) will also be presented. For categorical data, frequency count and percentages will be presented. Data listings will be provided for all subjects up to the point of withdrawal, with any subjects excluded from the relevant population highlighted. Summary statistics and statistical analyses will generally only be performed for subjects included in the relevant analysis population. For the calculation of summary statistics and statistical analysis, unrounded data will be used.

Mean change from baseline is the mean of all individual subjects' change from baseline values. Each individual change from baseline will be calculated by subtracting the individual subject's baseline value from the value at the timepoint. The individual subject's change from baseline values will be used to calculate the mean change from baseline using a SAS procedure such as Proc Univariate.

Data analysis will be performed using [REDACTED] or greater.

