Treprostinil PK sampling (IV period only)				2.5, 5, 10, and 30 minutes		Only for the study period when LY900014 is administered intravenously. Sampling times are relative to the time of study drug administration (time 0).
C-peptide samples				0, 30, 60, 120, 180, 240, 300, 360, 420, 480, 540, and 600 minutes		Sampling times are relative to the time of study drug administration (time 0).
Blood glucose sampling for euglycemic clamp				Approximately every 10 minutes for approximately 30 minutes before the start of dosing (for baseline measurement). During clamp, sampling occurs every 2.5 minutes for the first 30 minutes; every 5 minutes for 30 to 120 minutes; every 10 minutes for 120 to 480 minutes and every 20 minutes for 480 to 600 minutes.		Sampling times are relative to study drug administration (time 0). Glucose samples should be taken before PK samples. Failure to obtain samples due to clinical issues, such as problems with venous access, will not be considered a protocol violation. Repeat samples for counter-checking of apparent spurious results may be taken where indicated.
Pharmacogenetic sample		X				Period 1 only.
Immunogenicity sample				Predose of Periods 1 and 3	X	Additional samples may be collected if the investigator considers there is a possibility that an adverse event is immunologically indicated.
Discharge from CRU					X	Subjects will be discharged on Day 2.

Abbreviations: CRU = clinical research unit; ECG = electrocardiogram; ED = early discontinuation; FU = follow-up; IV = intravenous; PK = pharmacokinetics.

a Procedures should be performed at least 14 days after the last dose of study drug.

Note: The site should schedule activities as appropriate. In cases when several study procedures are scheduled at the same time, the order of priority will be as follows: glucose samples, PK samples, injection-site assessments, vital signs, ECG, clinical laboratory samples. If the investigator decides based on clinical judgment not to dose a subject on a given day (eg, because of low blood glucose), the subject's visit may be rescheduled; any procedures performed in that period may be repeated.

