### ***6.3.1. Meals and Dietary Restrictions***

For all treatment periods subjects will fast for at least 8 hours prior to dosing and until the glucose clamp procedure is completed, after which subjects will receive a meal. Water can be consumed freely during this time.

When not a resident at the CRU, subjects will be encouraged to follow their normal diets.

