### **9.6. Glucodynamics (Euglycemic Glucose Clamp)**

The aim of the euglycemic glucose clamp is to maintain target glucose levels through infusion of a 20% d-glucose (dextrose) solution after the administration of a dose of insulin. During the glucose clamp, the GIR will be adjusted to maintain a predetermined target blood glucose concentration for the individual subject. Thus, blood glucose concentrations are kept constant while the GIR varies. The varying GIR will then reflect the GD activity of insulin.

All glucose clamp procedures will be performed after an overnight fast of at least 8 hours. On the morning of each study period, a small catheter will be placed into a forearm vein, ideally at the elbow, for infusion of glucose. Another catheter will be placed at the wrist or hand or, in the case of difficult venous access, in the forearm as close to the wrist as possible for blood sampling. This area will be heated with a warming device to approximately 55°C to 60°C for sampling arterialized venous blood. Blood samples will be obtained at the bedside for immediate determination of whole blood glucose concentrations using an automated glucose oxidase technique or other appropriate analytical method. These glucose measurements shall be used for subject safety management as well as for GD evaluations.

The time of administration of LY900014 will be defined as time zero. Following completion of dosing, in conjunction with frequent blood sampling for measurement of blood glucose, 20% dextrose will be infused IV at a variable rate in order to maintain euglycemia up to 10 hours after LY900014 administration.

The clamp procedure will continue for up to 10 hours after dose or until after blood glucose concentrations return to baseline without any glucose being administered for at least 30 minutes, whichever is earlier.

Sampling for blood glucose should occur as described in the Schedule of Activities (Section 2). Repeat samples for counter-checking of apparent spurious results may be taken where indicated. Three or 4 predose glucose values will be used for calculation of mean predose fasting blood glucose (FBG) concentration.

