9.5.8 Other assessments

All other safety assessments not detailed in this section will be listed but not summarized or statistically analyzed.

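### Does the SAP leave the C-peptide objective unanswered, and would samples taken after a meal distort its profile?

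*SAP*

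**What the plan says.** SAP 4.3 lists as an exploratory objective "To evaluate C-peptide levels after administration of LY900014". Protocol Table ITRT.1 gives the same objective, with C-peptide concentrations as the endpoint. The Schedule of Activities sets the draws in every period at "0, 30, 60, 120, 180, 240, 300, 360, 420, 480, 540, and 600 minutes".

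After SAP 4.3, C-peptide does not appear in the PK, glucodynamic or safety sections. Protocol section 10 has no C-peptide analysis either. Three general statements in the SAP govern what is reported:

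- SAP 9.1 on summaries: "Summary statistics and statistical analysis will only be presented for data where detailed in this SAP".
- SAP 9.1 on listings: "Data listings will be provided for all data that is databased".
- SAP section 3: "If additional analyses are required to supplement the planned analyses described in this SAP, they may be performed and will be identified in the CSR".

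SAP 9.5.8 has a similar default, "All other safety assessments not detailed in this section will be listed but not summarized or statistically analyzed", but it is worded for safety assessments.

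On timing, Protocol 9.6 states "The clamp procedure will continue for up to 10 hours after dose or until after blood glucose concentrations return to baseline" with at least 30 minutes free of infused glucose, taking the earlier of the two. Protocol 6.3.1 has subjects fast "until the glucose clamp procedure is completed, after which subjects will receive a meal".

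**The concern.** An objective with a named endpoint appears to have no route to an answer. Forty-eight samples per subject are drawn for it, and a literal reading of SAP 9.1 stops at a listing. In healthy subjects, endogenous insulin could also contribute to the glucose infusion rate. No other scheduled assay bears on that, so leaving C-peptide unsummarised seems to weaken the reading of Rmax and Gtot.

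The second worry is about content. If a clamp stops early and the subject eats, the remaining C-peptide draws reflect the meal and not the response to LY900014. If clamps ended at different times after IV and SC dosing, a summary by nominal time would mix fasting and fed values unevenly across treatments.

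**Working it through.** **Sample count.** Inputs are the 12 times in the Schedule of Activities and the 2 mL volume in Protocol Appendix 4.

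- 12 samples × 4 periods = 48 samples.
- 48 × 2 mL = 96 mL, as Appendix 4 states.
- Share of the total: 96 / 399.8 = 24.0%, the largest single line.

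**Does the blood budget assume 10 hours of sampling?** Glucose draws per period are 12 (first 30 minutes, every 2.5) + 18 (30 to 120, every 5) + 36 (120 to 480, every 10) + 6 (480 to 600, every 20) = 72. Four predose values bring this to 76, which matches Appendix 4. The budget therefore covers sampling to 600 minutes in every period.

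**How many C-peptide samples could follow the clamp?** The documents give no clamp durations, so the end times below are assumptions. The count is the number of scheduled times later than the assumed end.

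| Assumed clamp end (min) | Samples after it, of 12 | Share |
|---|---|---|
| 240 | 6 | 50% |
| 300 | 5 | 42% |
| 360 | 4 | 33% |
| 420 | 3 | 25% |
| 480 | 2 | 17% |
| 540 | 1 | 8% |
| 600 | 0 | 0% |

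These are upper limits for fed samples, because a sample after the clamp is fed only if the meal came first. The Schedule places the 10-hour vital signs and ECG at the clamp's end, and Protocol 5.4 speaks of a 10-hour clamp. Both point to the last row. Protocol 9.6 allows the others. The two descriptions of when the clamp ends should be reconciled editorially, but no planned analysis turns on that.

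**What depends on C-peptide?** The primary analyses use insulin lispro AUC(0-∞). The secondary analyses use Rmax, Gtot, adverse events and injection-site reactions. None takes C-peptide as an input, covariate or exclusion criterion.

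**Can a post-clamp sample affect the reading of Rmax or Gtot?** An early end requires at least 30 minutes with no glucose given. Draws after that point lie outside the infusion that produces Rmax and Gtot. Draws during the clamp precede the meal.

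**Can an analyst fill the gap?** SAP 9.1 already sets the default statistics for continuous data and defines change from baseline. The 0-minute sample is the natural baseline. Protocol 9.6 requires infusion rates to be documented throughout, so the end of each clamp can be found. Because the meal comes only after clamp completion, cutting at clamp end removes every fed sample even if meal times were not recorded.

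**The case for a change.** The best argument for a change is that exploratory rank does not explain the silence. Treprostinil is the other exploratory objective, and SAP 9.3.1 gives it a stated focus on tmax and Cmax. C-peptide gets nothing, which looks like an oversight. Blood volume was also a live issue: amendment (a) added a weight and a hemoglobin criterion because about 400 mL would be drawn, and C-peptide takes 96 mL of it. Permission for extra analyses is not a plan, and a rule for samples after the clamp is best fixed before the data are seen.

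Part of this stands. The omission is real, and a short descriptive paragraph would have been tidier. The stronger claims do not stand:

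- SAP 9.1 limits the planned output. It does not forbid a summary, since SAP section 3 and Protocol 10.3.1 both allow additional analyses. The table and figure shells are a separate document, not available here, so whether they include C-peptide is unknown.
- Nothing in the documents shows that early stopping differs between IV and SC periods.
- The two halves of the concern do not combine: if the plan yields only a listing, there is no planned profile for fed values to distort.

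**Conclusion.** No change is needed. Followed to the letter, the plan lists the C-peptide concentrations, which are the stated exploratory endpoint, and every primary and secondary result is unaffected. What is missing is a descriptive summary that an analyst can produce from the listed data with SAP 9.1's default statistics. Any analyst plotting C-peptide against time would be expected to check clamp end first.

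The possible contamination runs from 0 to 6 of 12 samples per period over the assumed clamp ends, and is zero if clamps run the full 10 hours. It would apply only to an optional summary.

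This rests on two assumptions: that C-peptide is held in the study database (the SAP makes that exception only for ECGs), and that any later summary is identified in the study report as section 3 requires. If C-peptide were to be used to adjust or exclude glucodynamic results, a rule would have to be written beforehand, but the plan proposes no such use.
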